2.2.2 Kaplan-Meier Plots and Tables: Nominal Time for Event of Interest

The second set of K-M plots and tables were created for the above variables with nominal time (planned time of collection, e.g., 2 hours, 3 hours, etc.) used for clinical events of interest and actual time used for censoring events. Subjects were censored at the actual time of their first use of rescue medication or last reported data point if lost to follow-up. Subjects who did not have the clinical event of interest by 8 hours post dose were censored at 496 minutes (480 minutes + 15 minute window + 1 minute).

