⁹ Patients will be randomized in the IWRS system at the Baseline Visit (Randomization Day 01)

¹⁰ Patient should be instructed that the dose should be taken once the migraine attack reaches moderate or severe pain.

¹¹ Site staff to review and confirm entries with patients and confirm all data points are transferred to the system and reset eDiary for future patient use, PRIOR to the patient leaving the clinic.

¹² ± Windows for timeframe around efficacy assessments (15, 30, 45, 60, 90 min, 2, 3, 4, 6, 8, 24 and 48 hours) will be automated and captured in the eDiary.

¹³ These scales will be captured in the eDiary. Patients will also be asked about their most bothersome symptom at the time of reporting and treating a qualifying migraine.

¹⁴ Paper source document will be used to capture Migraine History. Patients will also be asked about their typical most bothersome symptom when having a migraine.

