2.2 Time to First Report of Absence of Various Symptoms

For each of the following variables, two sets of Kaplan-Meier plots and tables were created:

- Time to First Report of Absence of Most Bothersome Symptom
- Time to First Report of Absence of Nausea
- Time to First Report of Absence of Photophobia
- Time to First Report of Absence of Phonophobia
- Time to First Report of Return to Normal Functioning

The first set of plots and tables was similar to those created for the time to rescue medication (using actual time). For the second set of plots, nominal (planned time point) as opposed to actual time was used for clinical event times. Censoring was measured using actual time as in all previous plots.

For both sets of analyses, the analysis population for MBS and functional disability was the set of mITT subjects. The analysis population for nausea, phonophobia, and photophobia was the subset of mITT subjects that reported the symptom as present at the onset of their study migraine. The y-axis for all plots represents the probability of the occurrence of the event of interest, and therefore are increasing from left to right.

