2.2.1 Kaplan-Meier Plots and Tables: Actual Time for Event of Interest

The first set of K-M plots and tables were created using actual time of censoring and actual time for the clinical event of interest. Subjects were censored at the actual time of their first use of rescue medication or last reported data point if lost to follow-up. Subjects who did not have the clinical event of interest by 8 hours post dose were censored at 496 minutes (480 minutes + 15 minute window + 1 minute).

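### The nominal-time symptom Kaplan-Meier curves put events at planned times and rescue at actual times, so a report made after rescue can count as an event before it

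*SAP*

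**What the plan says.** SAP Appendix 3, section 2.2, defines two sets of curves and tables for time to first absence of the most bothersome symptom (MBS), nausea, photophobia and phonophobia, and for return to normal functioning.

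- **First set (2.2.1).** Both clocks agree: it is "created using actual time of censoring and actual time for the clinical event of interest".
- **Second set (2.2 and 2.2.2).** The clocks are split. "For the second set of plots, nominal (planned time point) as opposed to actual time was used for clinical event times", while "Censoring was measured using actual time as in all previous plots". Section 2.2.2 repeats the split, with planned time "used for clinical events of interest and actual time used for censoring events", and adds: "Subjects were censored at the actual time of their first use of rescue medication or last reported data point if lost to follow-up".
- **Late entries.** Subjects without the event by 8 hours are censored at 496 minutes, explained as "480 minutes + 15 minute window + 1 minute", so an 8-hour entry may come up to 15 minutes late. The 135-minute limit for pain relief up to 2 hours in SAP 5.7.6.2 implies the same allowance at 2 hours. Footnote 12 to the schedule of assessments (Protocol 4.3) gives every post-dose assessment a plus-or-minus window without stating its width.
- **Rescue.** Protocol 4.3.2 and 5.4.1 require the 2-hour diary entry before rescue. They set no such order for the later entries.
- **Rescue elsewhere in the SAP.** Section 2.3 (RM=F) and section 5.7.1 make evaluations at or after rescue failures. For the 3-hour endpoints, Appendix 3 sections 3.2, 4.1 and 4.2 judge this against the moment the subject provided the data.

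**The concern.** Moving an event back to its planned time while leaving rescue where it happened can swap their order. Take rescue at 182 minutes and a 3-hour entry at 190 minutes that first reports nausea absent. Section 2.2.2 read literally gives an event at 180 minutes, before the rescue. On actual times the subject is censored at 182. Under Appendix 3 section 4.1 the same entry makes the subject a failure for nausea freedom at 3 hours. One appendix would therefore classify one diary entry in two opposite ways.

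At stake are the nominal-time curves, tables and medians for five outcomes. A curve meant to describe relief before rescue could include reports made after it, and unequal rescue use could make the two arms differ in how often this happens.

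**Working it through.** **The plan's own figures.** 480 + 15 + 1 = 496 minutes, as stated. 120 + 15 = 135 minutes, which agrees with SAP 5.7.6.2.

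**The rule on single cases.** A subject has an event if the event time is no later than rescue; otherwise the subject is censored at rescue. Times are in minutes.

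| Planned | Entry | Rescue | Mixed clocks (2.2.2) | Actual times (2.2.1) |
|---|---|---|---|---|
| 180 | 194 | 185 | event at 180 | censored at 185 |
| 240 | 252 | 241 | event at 240 | censored at 241 |
| 480 | 495 | 482 | event at 480 | censored at 482 |
| 180 | 168 | 172 | censored at 172 | event at 168 |

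The first three rows are false pre-rescue events. The fourth is the opposite error, possible only if the window opens early. A false event at 2 hours needs rescue before the 2-hour entry, which the protocol does not allow.

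**How often rescue falls in the gap.** Assume entries 0 to 15 minutes late (mean 7.5) and rescue spread evenly over the 360 minutes from 2 to 8 hours. The gaps after 3, 4 and 6 hours then catch 3 × 7.5/360 = 6.25% of subjects rescued in that span. With rescue clustered early (exponential, mean 2 hours after hour 2), simulation gives 7.0%. Adding the 2-hour gap raises these to 4 × 7.5/360 = 8.3% and 13.3%. These are shares of rescued subjects, not of false events: a false event also needs the first report of absence to come at that very entry.

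**Share of all subjects misclassified.** Simulation of 400,000 subjects per setting. Assumptions, none of them in the documents: 10% to 40% of subjects take rescue, starting after the actual 2-hour entry with a mean delay of 90 minutes; the chance of first relief per assessment is 8% before rescue and 8% to 40% after; entry offsets are uniform, with one window width at every assessment.

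| Rescued | Relief chance after rescue | False events, 0 to +15 min | False events, ±15 min | Lost events, ±15 min |
|---|---|---|---|---|
| 10% | 8% | 0.03% | 0.02% | 0.04% |
| 10% | 40% | 0.17% | 0.08% | 0.04% |
| 40% | 8% | 0.14% | 0.06% | 0.15% |
| 40% | 40% | 0.70% | 0.33% | 0.15% |

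With the plan's 550 treated subjects per arm, 0.03% is 0.0003 × 550 = 0.2 subjects and 0.70% is 0.007 × 550 = 3.9 subjects. If some subjects take rescue after 120 minutes but before their 2-hour entry, the highest figure is 1.5%.

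**Effect on the comparison.** With a 0 to +15 minute window, suppose 40% take rescue in one arm and 10% in the other. False events then differ by 0.14 − 0.03 = 0.11 percentage points at the low relief rate and 0.70 − 0.17 = 0.53 points at the high one. With a ±15 minute window the two errors partly offset: in the 40% rescue rows the net is 0.06 − 0.15 = −0.09 and 0.33 − 0.15 = +0.18 points.

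**The case against.** The strongest reply is that SAP 5.7.1 already settles the matter. A 190-minute entry after rescue at 182 follows rescue, so it is a failure and never an event to be moved. Sections 3.2, 4.1 and 4.2 of Appendix 3 show the same intent, and section 2.2.2 may be read as choosing only the time axis. If the programs applied 5.7.1 on actual times first, no post-rescue report became an event. The documents do not show whether they did. The reply does not remove the point, because 5.7.1 is a failure rule for evaluations, whereas 2.2.2 states its own treatment of rescue, by censoring, and neither cites nor applies 5.7.1.

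Three further objections stand and limit the reach:

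- A reader might infer that these curves do credit rescue effects to study drug. The text shows only that post-rescue reports can be counted. Nothing in the documents attributes relief to rescue taken at most 15 minutes before the entry.
- A reader might take 8% to 13% as the share of misclassified subjects. Those figures describe rescued subjects whose rescue falls in a gap, and they include the 2-hour gap that the protocol closes.
- A reader might conclude that the nominal and actual-time curves differ because of misordering. They differ mainly by design, since every event not entered exactly on time is moved.

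**Conclusion.** The point holds as a defect in a stated rule with a conditional and probably small effect. As written, section 2.2.2 can turn a post-rescue report into a pre-rescue event at 3, 4, 6 or 8 hours, contrary to the SAP's other rescue rules. It can also lose a true event when an entry is early.

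The likely size is about 0.03% to 0.7% of subjects wrongly counted, or fewer than four per arm of 550. That range rests on assumed rescue and relief rates and on a 15-minute late allowance throughout, which the documents state only at 8 hours and imply at 2 hours. The direction of any net bias is not settled, because early entries work the other way.

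These are ad hoc supportive analyses outside the testing hierarchy of SAP 5.2.5. The co-primary and ranked secondary results do not use them, and the actual-time set keeps the true order for the same five outcomes.

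**What to change.** Add one clause to Appendix 3, section 2.2.2: event or censoring is decided on actual times first, and an event counts only if its actual report time precedes first use of rescue medication. Qualifying events are then plotted at nominal time. The derivation must keep a qualifying event even when rescue, though later than the report, falls before the nominal time, as in the fourth case above. Moving all censoring to the planned-time grid as well is optional and not needed to cure the misordering.

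The cost is one clause and a small change to the derivation. Since the appendix describes these analyses as done, it may also mean rerunning the nominal-time curves and tables for the five outcomes. If the programs already compared actual times, a confirming sentence is enough.

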3 PAIN AND MBS AT 3 HOURS POST DOSE

3.1 Pain Freedom at 3 Hours Post Dose

The between group difference in the percentage of subjects with pain freedom at 3 hours postdose was assessed by computing the "risk difference" between treatment groups. This was evaluated by computing the common risk difference, using CMH weights (sample size weights), stratified by the use of prophylactic migraine medication (yes or no). The risk difference was tested at a two-sided alpha level of 0.05. Missing data at 2 hours post-dose were imputed as failures (NC=F).

Results presented for this analysis included the following:

- Common risk difference with sample size, p-value, ASE, and 95% asymptotic CIs.
- Risk difference within each strata with sample size, p-value, ASE, and 95% asymptotic CIs.
- A plot of the risk differences within each strata, and common risk difference (similar to the risk difference plot produced by SAS Proc Freq).
- Common risk for each treatment with sample size, ASE, and 95% asymptotic CIs.

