2.3 Study Estimands

The tables that follow lay out the estimands corresponding to the study objectives. In these tables, the following abbreviations are used to describe the handling of intercurrent events for efficacy estimands:

NC=F: Non-Completers = Failure.

A subject with any missing data for an endpoint is classified as a treatment failure.

NC1=F: Non-Completers with more than 1 missing data point = Failure.

Subjects with more than 1 missing data point, other than at the 2, 24 or 48 hour data points, are classified as treatment failures. This applies to endpoints that are based on data from multiple time points. For example, for the durability endpoint of sustained pain freedom from 2 to 24 hours, the subjects should provide data at 2, 3, 4, 6, 8, and 24 hours. For NC1=F imputation, the data at 2 and 24 hour time points must be present or the subject is classified as a failure. However, any single data point may be missing at 3, 4, 6 or 8 hours without penalty. For sustained pain freedom from 2 to 48 hours, the data at 2, 24, and 48 hours are required to be present.

RM=F: Rescue Medication = Failure.

Subjects that take rescue medication before, or at, the time of the event of interest are classified as failures. If the time of rescue medication is missing, all events on or after the date of rescue medication are classified as failures.

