5.7.3.1 Pain Freedom at 2 Hours Post-Dose

Pain freedom is assessed using the number of mITT subjects that report pain levels of "none" at 2 hours post-dose on a 4-point Likert scale (0=none, 1=mild, 2=moderate, 3=severe). The information from the 4-point scale is directly summarized as follows:

- A table showing descriptive statistics for the observed data, which includes the number and percentage of subjects reporting each of the 4 pain levels at 2 hours post-dose, and the percentage of subjects with missing data, for each treatment group. The table will include exact (Clopper-Pearson) 95% CIs for each percentage.
 - This table will be repeated for Asian subjects only.

The estimand for the primary analysis is the percentage of pain free subjects. In statistical terms, this percentage is arrived at by estimating the probability or the "risk" that a subject is pain free.

The population summary, the between group difference in the percentage of pain free subjects is assessed by computing the "risk difference" between treatment groups. This is evaluated by computing the common risk difference, using Cochran-Mantel-Haenszel (CMH) weights (sample size weights), stratified by the use of prophylactic migraine medication (yes or no). The risk difference is tested at a two-sided alpha level of 0.05. Missing data at 2 hours post-dose will be imputed as failures (NC=F). If a stratum (prophylactic medication use: yes or no) has sparse data (less than 5 subjects), then the strata will be pooled.

Results presented for the primary analysis include the following:

- The number and percentage of subjects who are pain free, and those not pain free, at 2 hours post-dose. These are presented by stratum and treatment group, with asymptotic standard errors (ASE), and 95% asymptotic CIs.
- Common risk difference with sample size, p-value, asymptotic standard error (ASE), and 95% asymptotic CIs.
- Risk difference within each strata with sample size, p-value, asymptotic standard error (ASE), and 95% asymptotic CIs.
- A plot of the risk differences within each strata, and common risk difference (similar to the risk difference plot produced by SAS Proc Freq).
- Common risk for each treatment with sample size, ASE, and 95% asymptotic CIs.

The primary analysis will be repeated for the subgroups described in Section 5.2.6.

Sensitivity analyses will be conducted as follows:

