3.2 Freedom from MBS at 3 Hours Post Dose

The estimand, difference in percentage of subjects with freedom from MBS at 3 hours between treatment groups was evaluated by computing the common risk difference using CMH weights (sample size weights), stratified by the use of prophylactic migraine medication (yes or no). The risk difference was tested at a two-sided alpha level of 0.05. Missing data at 3 hours post-dose was imputed as failure (NC=F). Also the use of rescue medication prior to providing data at the 3 hour assessment, taking IP prior to reporting the MBS, or failure to report a MBS are events that were imputed as treatment failures.

Results presented for this analysis included the following:

- Common risk difference with sample size, p-value, ASE, and 95% asymptotic CIs.
- Risk difference within each strata with sample size, p-value, ASE, and 95% asymptotic CIs.
- A plot of the risk differences within each strata, and common risk difference (similar to the risk difference plot produced by SAS Proc Freq).
- Common risk for each treatment with sample size, ASE, and 95% asymptotic CIs.

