4 OTHER ENDPOINTS AT 3 HOURS POST DOSE

4.1 Freedom from Photophobia, Phonophobia, or Nausea at 3 Hours

Freedom from photophobia, phonophobia, and nausea were assessed, by treatment group, by tabulating the number of mITT subjects who reported the presence of the symptom at migraine onset, and later reported the absence of the symptom at 3 hours post-dose. Subjects who reported the symptom at baseline, but have missing data at 3 hours post-dose were imputed as failures (NC=F). Also, subjects in the analysis set who took rescue medications on or before providing their 3 hour post-dose data were imputed as failures.

The principal measurement for the associated symptoms (phonophobia, photophobia, and nausea) is made on a binary scale (0 = absent; 1 = present). An exploratory measurement of these symptoms was also made on a 4-point Likert scale (0=none, 1=mild, 2=moderate, 3=severe).

For these three endpoints, the difference between treatment groups, was evaluated by computing the common risk difference using CMH weights (sample size weights), stratified by the use of prophylactic migraine medication (yes or no). The risk difference was tested at a two-sided alpha level of 0.05.

Results presented for these analyses included the following:

- Common risk difference with sample size, p-value, ASE, and 95% asymptotic CIs.
- Risk difference within each strata with sample size, p-value, ASE, and 95% asymptotic CIs.

- A plot of the risk differences within each strata, and common risk difference (similar to the risk difference plot produced by SAS Proc Freq).
- Common risk for each treatment with sample size, ASE, and 95% asymptotic CIs.

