4.2 Pain Relief at 3 Hours Post Dose

Pain relief at 3 hours post-dose was assessed by tabulating the number of mITT subjects that reported a pain level of none or mild (responses of 0 or 1 on the 4-point Likert scale) at 3 hours post-dose by treatment group. Subjects with missing data at 3 hours post-dose were imputed as failures (NC=F). Also, subjects in the analysis set who took rescue medications on or before providing their 3 hour post-dose data were imputed as failures.

Results presented for this analysis included the following:

- Common risk difference with sample size, p-value, ASE, and 95% asymptotic CIs.
- Risk difference within each strata with sample size, p-value, ASE, and 95% asymptotic CIs.
- A plot of the risk differences within each strata, and common risk difference (similar to the risk difference plot produced by SAS Proc Freq).
- Common risk for each treatment with sample size, ASE, and 95% asymptotic CIs.

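### SAP Appendix 3, section 3.1, ties the failure rule for 3-hour pain freedom to scores missing at 2 hours instead of 3 hours

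*SAP*

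**What the plan says.** SAP Appendix 3, section 3.1, leaves no doubt about its endpoint: "The between group difference in the percentage of subjects with pain freedom at 3 hours postdose was assessed". The comparison is a common risk difference with CMH weights, stratified by prophylactic medication, and "The risk difference was tested at a two-sided alpha level of 0.05". The next sentence gives the missing-data rule: "Missing data at 2 hours post-dose were imputed as failures (NC=F". The section has no other sentence on missing data.

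The other 3-hour sections of the appendix that state a missing-data rule use the 3-hour value:

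- MBS freedom, section 3.2: "Missing data at 3 hours post-dose was imputed as failure (NC=F".
- Photophobia, phonophobia and nausea, section 4.1: subjects who "have missing data at 3 hours post-dose were imputed as failures (NC=F".
- Pain relief, section 4.2: "Subjects with missing data at 3 hours post-dose were imputed as failures (NC=F".

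The general definition of NC=F in SAP 2.3 is "A subject with any missing data for an endpoint is classified as a treatment failure". The wording in section 3.1 closely matches the rule for the 2-hour co-primary endpoint in SAP 5.7.3.1, where it is correct: "Missing data at 2 hours post-dose will be imputed as failures (NC=F".

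**The concern.** The 2-hour and 3-hour pain scores are separate eDiary entries (Protocol 4.3.2 and Table 1), so either can be missing without the other. Taken at its word, section 3.1 does two things that the 3-hour endpoint does not call for. It turns an observed 3-hour success into a failure when the 2-hour entry is absent, and it does not state what becomes of a subject whose 3-hour score is absent.

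Appendix 3 is written in the past tense, and SAP section 7 says that the supportive analyses were conducted. The sentence is therefore the record of what was done, and a reader cannot tell from it which time point stands behind Table 14.2.3.18.1. The 3-hour pain and MBS analyses sit under one heading and mirror the co-primary pair, so a reader will expect one rule for both. Missing diary entries are also a live topic here: SAP 5.6 tabulates missing pain data at each time point from 2 to 48 hours and splits the table by the date of an eDiary software fix.

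**Working it through.** The documents state no figure for the 3-hour analysis, so there is none to reproduce. The check is a comparison of texts, followed by an illustration of size.

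**Comparison.**

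| SAP place | Endpoint | Missing score that counts as failure |
|---|---|---|
| 5.7.3.1 | Pain freedom, 2 h | 2 h |
| Appendix 3, 3.1 | Pain freedom, 3 h | **2 h** |
| Appendix 3, 3.2 | MBS freedom, 3 h | 3 h |
| Appendix 3, 4.1 | Photophobia, phonophobia, nausea, 3 h | 3 h |
| Appendix 3, 4.2 | Pain relief, 3 h | 3 h |
| 2.3 (NC=F) | General | Any data missing for the endpoint |

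Section 3.1 is the only row in which the endpoint and the rule refer to different times. The likeliest explanation is that the sentence was carried over from 5.7.3.1 without changing the hour.

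**Inputs for the illustration.** About 550 subjects per arm (SAP 5.1). Pain-free rates of 31.4% and 15.3% (Protocol 1.3.2.8), a difference of 16.1 points. These are 2-hour Phase 2b rates standing in for 3-hour rates, which are not given. Assumed: a fraction m2 missing at 2 hours (2-10%) and m3 at 3 hours (2-15%), equal in both arms, independent of each other and of response.

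**Formulas.**

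- 3-hour rule: RD = 16.1 x (1 - m3).
- Literal rule, with 2-hour missing failed and subjects missing only at 3 hours excluded: RD = 16.1 x (1 - m2)(1 - m3) / [1 - (1 - m2) x m3].

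| m2 | m3 | 3-hour rule | Literal rule | Shift (points) |
|---|---|---|---|---|
| 2% | 2% | 15.78 | 15.77 | -0.01 |
| 5% | 5% | 15.30 | 16.1 x 0.9025/0.9525 = 15.25 | -0.04 |
| 10% | 10% | 14.49 | 16.1 x 0.81/0.91 = 14.33 | -0.16 |
| 10% | 2% | 15.78 | 16.1 x 0.882/0.982 = 14.46 | -1.3 |
| 2% | 15% | 13.69 | 16.1 x 0.833/0.853 = 15.72 | +2.0 |

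Failing subjects for a missed 2-hour entry lowers the difference; excluding those missing at 3 hours raises it. At equal missingness the two nearly cancel.

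**Subjects involved.** Observed pain free at 3 hours but failed for a missed 2-hour entry: 550 x m2 x (1 - m3) x rate, about 3 to 17 on rimegepant and 1 to 8 on placebo. Present at 2 hours but missing at 3 hours, for whom section 3.1 names no outcome: 550 x (1 - m2) x m3, about 10 to 81 per arm.

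**Dependence on the exclusion assumption.** The text does not say that these subjects are excluded. If they stay in the denominator as failures and the 2-hour rule is applied as well, RD = 16.1 x (1 - m2)(1 - m3). The shift is then -m2 x 16.1 x (1 - m3), from -0.02 x 13.69 = -0.3 to -0.10 x 15.78 = -1.6 points. There is no cancellation in that case, and the shift is always towards no difference. If the same subjects miss both entries, the literal rule and the 3-hour rule give the same result.

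**The case against.** The strongest reply is that this is a one-word slip whose intent nobody could mistake. The sentence carries the NC=F label. SAP 2.3 defines that label by data missing for the endpoint, and for this endpoint that is the 3-hour score. SAP 2.3 introduces the abbreviation for its estimand tables, which do not list 3-hour pain freedom, but the SAP offers no other meaning. Appendix 4 lists the table on mITT subjects, so nothing says that anyone is dropped. All of this stands. A reader might infer that missing 3-hour data have no handling at all; the documents do not support that. They contain a conflict between a label and a stated hour, and the label points to the right answer.

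A reader might also infer that rescue between 2 and 3 hours is ignored, because section 3.1 omits the rescue sentence found in 3.2, 4.1 and 4.2. That does not hold either. SAP 5.7.1 makes any efficacy evaluation at or after rescue a failure, and the SAP often leaves the rule unrepeated, for example in 5.7.3.1 and 5.7.4.2.

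Nor does it follow that the 3-hour pain and MBS results cannot be compared. Under SAP 2.3 and 5.7.1 they share the same rules; only the literal reading separates them.

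What the reply does not remove is that an analysis rule, as written, names the wrong time point, and that the documents cannot show which one the program used.

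**Conclusion.** The point holds as a wording error in a stated analysis rule. Section 3.1 conflicts with the SAP's own NC=F definition and with three parallel sections.

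Any size rests on assumed missingness and stand-in response rates. With 2-10% missing at 2 hours and 2-15% at 3 hours, and with subjects missing at 3 hours excluded, the risk difference moves by about -1.3 to +2.0 points and is almost unchanged when missingness is equal. If those subjects are instead kept as failures, the shift is about -0.3 to -1.6 points. The documents therefore support neither a particular size nor a consistent bias in favour of rimegepant.

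It would also go too far to conclude that the reported table is wrong: that is so only if the program followed the sentence literally. The analysis is labelled ad hoc (SAP Appendix 4), is supportive (SAP section 7) and lies outside the co-primary family and the fixed sequence in SAP 5.2.5. No confirmatory conclusion, type I error or power depends on it. The correction is worth making but minor.

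**What to change.** In SAP Appendix 3, section 3.1, change 2 hours to 3 hours in the missing-data sentence. Check which time point the program for Table 14.2.3.18.1 used, and re-run the table if it was not the 3-hour score. No new rescue rule is needed; a cross-reference to SAP 5.7.1 would be optional. If the SAP is already final, a note in the clinical study report stating the rule actually applied would serve the same purpose. The cost is one word and a program check, plus one table re-run at most.
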